1.3. Rationale for the Dose Selection

Remdesivir has been approved for the treatment of COVID-19 in Japan, the EU, and the US at an initial dose of 200 mg IV followed by 100 mg IV for the next 4 or 9 days. This protocol proposes investigation of a new route of administration through the respiratory tract to deliver drug directly to the primary site of infection while reducing overall systemic exposure.

Safety, tolerability, and PK of RDV administered via inhalation are being evaluated in an ongoing Phase 1a study in healthy participants (GS-US-553-9018). Two different RDV formulations, Remdesivir for Injection formulation and Remdesivir for Inhalation Solution formulation, were evaluated in this study at the nominal doses up to 62 mg (estimated 10 mg deposited dose, administered using LC[®] Sprint (PARI Respiratory Equipment, Inc.) equipped with sealed facemask and an exhaust filter, 16.1% to 17% device efficiency) once daily for 5 days. Safety and preliminary PK data are available for the Remdesivir for Injection formulation, and PK and safety results for Remdesivir for Inhalation Solution formulation are forthcoming. An amendment to protocol GS-US-553-9018 is ongoing to generate additional safety and PK data for LC Sprint equipped with mouthpiece, and Remdesivir for Inhalation Solution formulation. This additional cohort is planned to run in parallel to Part C of the GS-US-553-9020 study, and together will inform on the Phase 3 dose selection for inhaled RDV. Both formulations were well tolerated in the healthy volunteer study up to 62 mg nominal dose (10 mg deposited). Preliminary data are discussed in Section 1.2.2.1.

Based on these results, 31 mg and 62 mg doses are proposed for evaluation in Parts A and B of the current study, respectively. Briefly, a nominal dose of 31 mg Remdesivir for Injection formulation (estimated 5 mg deposited dose; utilizing 16.1% device efficiency) for 3 or 5 days is proposed for evaluation in Part A. This dose is predicted to achieve similar concentrations of the active GS-443902 in respiratory tissues as those expected following a 100 mg human IV dose. A higher nominal dose of 62 mg (estimated 10 mg deposited dose; utilizing 16.1% device efficiency), which may provide increased efficacy when administered to patients, is proposed for Part B. In both Parts, RDV will be administered using LC Sprint equipped with sealed facemask and an exhaust filter.

Part C:

Remdesivir for Inhalation Solution formulation and a new device configuration of LC Sprint utilizing a mouthpiece for drug delivery will be evaluated in Part C. This new formulation contains reduced levels of an excipient, SBEC (7.5% after reconstitution, as compared to 15% for Remdesivir for Injection formulation), which may offer improved safety when RDV is administered via inhalation. Both the new formulation and the new device configuration are being evaluated in healthy participants: Cohort 6 (60 mg Remdesivir for Inhalation Solution formulation or placebo, for 5 days, inhaled via sealed facemask) and Cohort 7 (39 mg Remdesivir for Inhalation Solution formulation or placebo, single dose, inhaled via mouthpiece). In alignment with the doses evaluated in the healthy volunteers study, the nominal dose in Part C is projected to be 39 mg (estimated 10 mg deposited dose; utilizing 25.6% mouthpiece configuration efficiency).

The proposed doses for evaluation in Part A, B, and C are anticipated to be safe and efficacious, based on the cumulative clinical and nonclinical information available to date (Section 1.2.2.1 and inhalation IB). Estimated dose margins based on mg/g lung weight at the lowest and highest nominal doses evaluated in this study are 5.2- and 2.6-fold, respectively (inhalation IB).

Duration of 3 to 5 days of dosing will be evaluated in this study. The 5-day dosing duration is the recommended IV remdesivir duration for treatment of COVID-19 requiring hospitalization and not requiring invasive mechanical ventilation and/or extracorporeal membrane oxygenation {[VEKLURY 2020](#)}. Shorter treatment duration of IV RDV for 3 days is currently being evaluated in an outpatient study (GS-US-540-9012) in COVID-19 patients at risk for disease progression.

1.4. Risk/Benefit Assessment for the Study

Potential risks of a participant's study involvement include unknown adverse events (AEs) due to inhaled RDV. Strategies to mitigate these risks include close monitoring of participant's clinical status and laboratory testing. Parameters for discontinuation of the study treatment due to AEs will be well defined and closely followed.

Transient, Grade ≤ 2, treatment-emergent elevations in alanine aminotransferase (ALT) and aspartate aminotransferase (AST) were observed with daily IV RDV administration in Phase 1 studies in healthy volunteers. Transaminases increased is a listed adverse drug reaction to RDV. However, due to the reduced systemic exposure to RDV compared to the IV regimen, it is anticipated that there will be a lower effect on ALT and AST. Nonetheless, liver function testing will be closely monitored during the study.

Remdesivir contains SBECID, an approved excipient. In nonclinical species, SBECID administration has been associated with kidney vacuolation and hypertrophy. However, nonclinical inhalation toxicology studies and available inhaled clinical data with SBECID support its use in the RDV clinical formulation.

Participants may or may not clinically benefit from participation in the study. If efficacious, benefits might include shorter duration or lower severity of COVID-19 symptoms or reduced progression to severe disease. They may also benefit from increased observations and evaluations by health care professionals. Data from this study may support further evaluation of inhaled RDV in patients with COVID-19.

During a pandemic, additional potential risks to participants may include adequate study treatment availability, interruptions to the study visit schedule, and adherence to protocol-specified safety monitoring or laboratory assessments. Refer to [Appendix 2](#) for further details on the risks and risk mitigation strategy.

Considering the above, the benefit-risk balance for this study is considered positive.

1.5. Compliance

This study will be conducted in compliance with this protocol, Good Clinical Practice (GCP), and all applicable regulatory requirements.

2. OBJECTIVES

The primary objective of this study is:

- To characterize the impact of inhaled RDV on SARS-CoV-2 viral load in participants with early stage COVID-19

The secondary objectives of this study are:

- To evaluate the safety and tolerability of inhaled Remdesivir for Injection formulation in participants with early stage COVID-19
- To evaluate the PK of inhaled Remdesivir for Injection formulation and its metabolites in participants with early stage COVID-19 in Parts A and B
- To characterize and evaluate disease progression from baseline
- To characterize the efficacy, safety, and tolerability of Remdesivir for Inhalation Solution formulation administered with a mouthpiece in Part C of the study

CCI

3. STUDY DESIGN

3.1. Endpoints

The primary endpoint of this study is:

- Time weighted average change in SARS-CoV-2 viral load which is defined as AUC of viral load change divided by time between baseline through Day 7

The secondary endpoints of this study are:

- Proportion of participants with treatment-emergent AEs (TEAEs) and laboratory abnormalities
- Proportion of participants with TEAEs leading to study treatment discontinuation
- Composite of all-cause medically attended visits (MAVs) (medical visits attended in person by the participant and a health care professional) or death by Day 28
- Composite of COVID-19 related MAVs (medical visits attended in person by the participant and a health care professional) or death by Day 28
- Proportion of participants hospitalized by Day 28
- Characterization of the plasma concentrations of inhaled RDV and its metabolites including AUC_{0-24h} , AUC_{last} , $CL_{ss/F}$, $t_{1/2}$, $V_{z/F}$, C_{max} , T_{max} , C_{last} , T_{last} , AUC_{tau} , λ_z , and C_{tau} (Parts A and B only)
- Change in SARS-CoV-2 viral load from baseline to Day 5
- Change in SARS-CoV-2 viral load from baseline to Day 7
- Change in SARS-CoV-2 viral load from baseline to Day 14 (Parts A and B only)
- Time to negative SARS-CoV-2 polymerase chain reaction (PCR)
- Time to alleviation (mild or absent) of baseline COVID-19 symptoms as reported on the COVID-19 adapted InFLUenza Patient-Reported Outcome (FLU-PRO[®]) questionnaire

CCI

■ [REDACTED]
■ [REDACTED]
■ [REDACTED]
■ [REDACTED]

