8.5.2. Secondary Analyses

The proportion of participants all-cause MAV (medical visits attended in person by the participant and a health care professional) or death by Day 28 will be estimated using Kaplan-Meier methods by treatment group in Part C. The proportion of participants COVID-19 related MAVs or death by Day 28 will be estimated using Kaplan-Meier methods by treatment group in Part C. The proportion of hospitalization by Day 28 will be summarized by treatment group. Kaplan Meier product limit method will be used to estimate time to negative SARS-CoV-2 PCR and time to alleviation (mild or absent) of baseline COVID-19 symptoms by treatment group.

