3.8. Analysis Visit Windows

3.8.1. Definition of Study Day

Study Day 1 is defined as the first dosing date of study drug.

Study Days are calculated relative to Study Day 1 and derived as follows:

- For postdose study days: Assessment Date – First Dosing Date + 1
- For days prior to the first dose: Assessment Date – First Dosing Date

Therefore, **Study Day 1/ First Dose Date** is the day of first dose of study drug administration, as recorded on the Study Drug Administration eCRF form.

Last Dose Date is defined as the maximum, nonmissing, nonzero dose end date of treatment recorded on the Study Drug Administration eCRF form with “Study Drug Permanently Withdrawn” box checked for participants who prematurely discontinued or completed study drug according to the Study Drug Completion eCRF.

Last Study Date is the latest of the study drug start dates and end dates, the clinic visit dates, FLU-PRO questionnaire collection date, and the laboratory visit dates, including the 28-day follow-up visit date, and the death date (if applicable, only for participants who prematurely discontinued study according to the Study Completion eCRF).

Baseline value is defined as the last value obtained on or prior to the first dose date (and time, if available) unless otherwise specified (see Section [3.8.3](#)).

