6.2.1. Analysis of Secondary Efficacy Endpoints

The FAS will be the primary analysis set for hospitalizations, MAVs and FLU-PRO questionnaire analyses. The mFAS will be the primary analysis set for SARS-CoV-2 viral load analyses.

Composite Endpoint of All-Cause MAVs or All-Cause Death by Day 28

The proportion of participants with all-cause MAVs or all-cause death by Study Day 28 will be estimated using Kaplan-Meier methods by treatment group and compared among 3 treatment groups in Part A and Part B and between the 2 treatment groups in Part C using a log-rank test.

If participants have no event by Study Day 28, participants will be censored at date of earlier of Study Day 28 and last study day. If a participant has a MAV first and then dies, then date of the MAV and status will be used for this participant.

Composite Endpoint of COVID-19 Related MAVs or All-Cause Death by Day 28

The proportion of participants with COVIS-19 related MAVs or all-cause death will be analyzed using the same method as used for composite endpoint of all MAVs or all-cause death by day 28.

In addition, a summary by pooled RDV and Pooled PTM may be provided and compared using CMH method including Part as strata in the model.

Proportion of participants hospitalized by Day 28

The proportion of participants with all-cause hospitalization (ICU, non-ICU, or unknown ward from Hospitalization/MAVs CRF) by Study Day 28 will be estimated using the Kaplan-Meier method and compared among treatment groups using a log-rank test. The time to all-cause hospitalization is defined using the first hospitalization date by Study Day 28, depending on which happens first. If participants have no event by Study Day 28, participants will be censored at date of earlier of Study Day 28 and last study day/death.

Time to Negative SARS-CoV-2 PCR

Negative SARS-CoV-2 PCR based on RT-PCR viral load is defined as:

- (1) the results reported as ‘No SARS-CoV-2 detected’, AND
- (2) two consecutive negative results, or negative at last available sample for participants who completed or discontinued from study.

The time to negative SARS-CoV-2 PCR is defined (in days) as the number of days to first confirmed negative:

First date of two consecutive dates achieving negative result – First dose date +1.

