- i. The month and year (or year) of onset date is the same as or after the month and year (or year) of the first dose of study drug, and
- ii. The month and year (or year) of the onset date is the same as or before the month and year (or year) of the 30th day after the date of the last dose of study drug, and
- iii. End date is as follows:

The (complete) end date is on or after the first dose date, or

The month and year (or year) of end date is the same or after the month and year (or year) of the first dose of study drug, or

End date is completely missing

Events with Completely Missing Onset Date

An AE with a completely missing onset date is defined as TEAE if end date meets any of the 3 criteria specified above.

10) The precision in reporting numerical values should be as follows:

Raw measurements will be reported the same as the data captured electronically or on the eCRF for all.

Standard deviation and standard error will be reported to one more significant decimal place than the raw measurement.

Mean, median, minimum, Q1, Q3, and maximum will be reported to the same number of decimal places of the raw measurements.

Exceptions may be considered; for example, if more than 4 significant digits are provided for the measurement.

Precision for derived parameters will be kept as 8 decimals and in listings 2 decimals will be kept.

Precision for derived parameters as follows:

Parameters	Decimal Places
log 10 of SARS-CoV-2 viral load	2
Time-weighted average change in SARS-CoV-2 viral load	2
BMI	2

- 11) Last dose date is not expected to be missing. However, if last dose date is missing, it will be imputed using the maximum of non-missing, non-zero dose, study drug start and stop dates.
- 12) Incomplete death dates will be imputed as the maximum of the study drug start dates (lasfdt), study drug end dates (lasldt), clinic visit dates (lvis28dt), laboratory visit dates (llab28dt), including the 28-day follow-up visit date plus 1, ie dthdt = $\max(\text{lasfdt}, \text{lasldt}, \text{lvis28dt}, \text{llab28dt}) + 1$.
- 13) Censoring rules

Time to hospitalization: If a participant prematurely discontinues from the study prior to Day 28 or the hospitalization status is missing, the participant is censored at last study date or day 28 whichever is earlier.

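### SAP 6.2.1 estimates the proportion hospitalized by Day 28 by Kaplan-Meier with death censored, which slightly overstates that proportion when an unadmitted death precedes a later admission in the same arm

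*Protocol*

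**What the plan says.** The protocol defines the endpoint as "Proportion of participants hospitalized by Day 28" (Protocol 3.1, repeated in 8.1.3). Death is not part of it. For the analysis, Protocol 8.5.2 says: "The proportion of hospitalization by Day 28 will be summarized by treatment group". The same paragraph assigns Kaplan-Meier methods to the two MAV composites, time to negative PCR and time to symptom alleviation, but not to hospitalization.

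SAP 6.2.1 goes further. The proportion hospitalized "by Study Day 28 will be estimated using the Kaplan-Meier method and compared among treatment groups using a log-rank test". The event is admission alone: "The time to all-cause hospitalization is defined using the first hospitalization date by Study Day 28". For those with no admission, "participants will be censored at date of earlier of Study Day 28 and last study day/death".

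SAP Appendix 2, item 13, covers participants who leave the study before Day 28 or whose hospitalization status is missing: "the participant is censored at last study date or day 28 whichever is earlier". SAP 3.8.1 builds Last Study Date from a list of dates, "including the 28-day follow-up visit date, and the death date"; the death date is used for participants who left the study prematurely. So the appendix rule also censors at death.

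The text available names no competing-risk estimator for this endpoint.

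**The concern.** Kaplan-Meier assumes that a censored participant would have gone on to have the event at the same rate as those still under observation. That is reasonable for someone lost to follow-up. It is false for someone who has died, whose chance of a later admission is zero. Censoring the death takes that person out of the later denominators, and each subsequent admission then carries too much weight. The result is a percentage for a hypothetical population in which nobody dies before admission, not the share of participants who were actually hospitalized.

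What is at stake is whether the reported percentage is the quantity the protocol names. The groups are small, so one participant shows in the result.

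**Working it through.** **Inputs.** Neither document gives an event rate or a planned figure for this endpoint, and SAP 1.4 says no power calculation was done, so there is nothing to reproduce. Group sizes follow from Protocol 3.3: Parts A and B, 36/3 = 12 per group; Part C, 80 x 3/4 = 60 on remdesivir and 80 x 1/4 = 20 on placebo. The counts of admissions and deaths below are assumptions.

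**Formulas.** Let a group of n have d deaths without admission, all before h first admissions at distinct times, with everyone else followed to Day 28.

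- SAP rule: 1 - KM = 1 - (1 - 1/(n-d)) x (1 - 1/(n-d-1)) x ... over the h admissions, which reduces to h/(n-d).
- Aalen-Johansen: the sum over admissions of (probability of being alive and unadmitted just before) x (1/number at risk), which reduces to h/n, the crude proportion.
- Excess: h/(n-d) - h/n = hd/[n(n-d)].

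**One case in full.** n = 20, death on Day 8, admission on Day 12. Nineteen are at risk on Day 12, so 1 - KM = 1/19 = 5.26%. Aalen-Johansen = (19/20) x (1/19) = 5.00%. The excess is 1/380 = 0.26 percentage points.

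**Other assumed cases.**

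| n | Admissions | Unadmitted deaths | SAP 1 - KM | Aalen-Johansen = crude | Excess (points) |
|---|---|---|---|---|---|
| 12 | 1 | 1, earlier | 1/11 = 9.09% | 1/12 = 8.33% | 0.76 |
| 20 | 2 | 1, earlier | 2/19 = 10.53% | 2/20 = 10.00% | 0.53 |
| 60 | 3 | 2, earlier | 3/58 = 5.17% | 3/60 = 5.00% | 0.17 |
| 60 | 3 | 2, after the last admission | 5.00% | 5.00% | 0 |
| 20 | 0 | 1 | 0% | 0% | 0 |
| any | any | none | h/n | h/n | 0 |

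The excess needs an unadmitted death and a later admission in the same group. Under 1 point describes these cases and is not a general bound: two earlier deaths and one admission in a group of 12 would give 1/10 = 10.0% against 1/12 = 8.3%, or 1.7 points.

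The row with one death and no admission shows that Kaplan-Meier, Aalen-Johansen and the crude proportion all return 0%. Hospitalization or death would give 1/20 = 5.0%, but that is a different endpoint.

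**The case against.** The strongest case against making a point of this has four parts.

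- **Death is covered elsewhere.** For the all-cause composite, SAP 6.2.1 says: "The proportion of participants with all-cause MAVs or all-cause death by Study Day 28 will be estimated using Kaplan-Meier methods". The COVID-19-related composite follows the same method. SAP 7.1.7 also summarizes deaths from first dose to 30 days after last dose, which spans Day 28, and lists all deaths. This stands: no death disappears from the report.
- **The log-rank test is sound.** Censoring at a competing event gives a valid test of the cause-specific hazard of admission. This stands; only the percentage is affected.
- **The setting makes the problem rare.** Participants are outpatients with SpO2 above 94% and no need for hospitalization at entry, and the endpoint is an unpowered secondary one. This stands, and it limits the importance of the point.
- **Kaplan-Meier handles early withdrawal, which a plain proportion does not.** This is a fair reason not to revert to the crude proportion alone. It does not justify censoring deaths, because Aalen-Johansen handles withdrawal equally well.

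A reader might infer something stronger: that the SAP wrongly scores the worst outcome as no event. The documents do not support this. The protocol endpoint is hospitalization alone, so any faithful estimate of it scores a death at home as no hospitalization. The gap between 5.3% and 2/20 = 10.0% in the group of 20, or between 9.1% and 2/12 = 16.7% in the group of 12, comes mainly from changing the endpoint and does not measure Kaplan-Meier bias.

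**Conclusion.** The point holds as a minor correction to the estimator. The SAP's stated rule does not return the proportion the protocol names when an unadmitted death precedes a later admission in the same arm, and the error is always upward. In the single-death, single-admission cases it is 0.26 points for n = 20 and 0.76 points for n = 12. It is nil if nobody dies unadmitted, or if all such deaths follow the last admission.

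This rests on the assumed counts, on otherwise complete follow-up, and on a death before Day 28 being recorded as premature discontinuation, so that Last Study Date takes in the death date.

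The point does not extend to the log-rank comparison or to the choice of endpoint, and it does not mean that deaths go unreported.

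**What to change.** In SAP 6.2.1 and Appendix 2, item 13:

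1. Report the proportion hospitalized through Day 28 as the Aalen-Johansen cumulative incidence, with death before admission as a competing event. Continue to censor at withdrawal or loss to follow-up. When follow-up is otherwise complete this equals the crude proportion.
2. Show the number of deaths without admission by treatment group beside it.
3. Keep the log-rank test and label it a comparison of cause-specific hazards.
4. Optionally add hospitalization or death from any cause as a supportive analysis. It should not replace the endpoint, because that would redefine a protocol secondary endpoint in the SAP.

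Striking the word for death from the 6.2.1 censoring rule would not be enough: the last study day left in that rule already takes in the death date through SAP 3.8.1. Death has to be coded as a competing event.

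The SAP already uses the hospitalization and death dates, so no new data are needed. The cost is a few sentences, a programming option and an added table row.

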3.2. Study Design

This study is a randomized, blinded, placebo-controlled, multicenter study of inhaled RDV in participants with early stage COVID-19 infection. In Parts A and B of the study, eligible participants will be randomized in equal proportions to 1 of 3 treatment groups.

Part C of this study is a randomized, blinded, placebo-controlled, multicenter study of Remdesivir for Inhalation Solution formulation in participants with early stage COVID-19 infection. Eligible participants will be randomized in a 3:1 ratio to 1 of 2 treatment groups to receive Remdesivir for Inhalation Solution formulation or PTM administered by mouthpiece.

The term “inhaled remdesivir” refers to both the Remdesivir for Injection formulation and Remdesivir for Inhalation Solution formulation when administered via nebulization using the LC Sprint.

